 - i. Frequencies assessed: 250-8000 Hz, including all inter-octaves
- b. Speech Perception Measures
 Speech perception will be assessed in an aided (cochlear implant speech processor on) and unaided (cochlear implant speech processor off) condition.
 Recorded materials will be presented at 60 dB SPL.
 - i. Speech Perception in Quiet
 - a. Listening condition
 - i. Speech 0° azimuth
 - b. Speech perception materials
 - i. CNC words
 - ii. CID sentences
 - iii. HINT sentences (if >50% correct on CID sentences)
 - iv. AzBio sentences (if >50% correct on HINT sentences)

- ii. Speech Perception in Noise
 - a. Listening conditions
 - i. Speech and noise 0° azimuth
 - ii. Speech 0° azimuth and noise to implanted side
 - iii. Speech 0° azimuth and noise to contralateral ear
 - b. Speech perception materials
 - i. HINT sentences
 - a. If >50% at SNR+10, then SNR+5
 - b. If >50% at SNR+5, then SNR+0
 - ii. AzBio sentences
 - a. If >50% at SNR+10, then SNR+5
 - b. If >50% at SNR+5, then SNR+0
 - iii. BKB-SIN sentences with adaptive SNR
- iii. Listening Conditions
 - a. Cochlear implant only (contralateral ear masked)
 - b. Contralateral ear only (cochlear implant speech processor off)
 - c. Combined (Cochlear implant on + contralateral ear unmasked)
- c. Localization

Localization will be assessed in an aided (cochlear implant speech processor on) and unaided (cochlear implant speech processor off) condition.

- i. The stimulus is a 200-ms speech-shaped noise, presented at 70dB-SPL from one of the 11 speakers (evenly spaced -180 to 180 degrees), selected at random.
- ii. The listener will be facing the center speaker during stimulus presentation. The task is to identify the source of the noise via a touchscreen monitor. No feedback is provided.
- iii. Data will be analyzed in terms of error and adjusted constant error, as described by Grantham et al (2007).
- iv. Listening Conditions
 - a. Contralateral ear only (cochlear implant speech processor off)
 - b. Combined (Cochlear implant on + contralateral ear unmasked)
- 4. Subjective questionnaires
 - a. Speech, Spatial and Qualities of Hearing Scale (SSQ) Gatehouse & Noble (2004)
 - b. Abbreviated Profile of Hearing Aid Benefit (APHAB) Cox & Alexander (1995)

VII. Proposed Claims

- A. Demonstrate the safety and effectiveness of cochlear implantation in populations suffering from unilateral profound hearing loss after labyrinthectomy or translabyrinthine surgical approaches.

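### HINT and AzBio are given only after >50% on an easier step, but the planned repeated-measures ANOVA has no rule for steps not given, so some of these scores can be analysed in a subset of the 10 chosen by their own scores

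*Combined protocol and SAP*

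**What the plan says.** Section VI.C.3.b sets two ladders.

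- Quiet: CNC and CID have no condition. Then come "HINT sentences (if >50% correct on CID sentences") and "AzBio sentences (if >50% correct on HINT sentences").
- Noise: the same two rules stand under both HINT and AzBio, "If >50% at SNR+10, then SNR+5" and "If >50% at SNR+5, then SNR+0". The third noise test has no gate: "BKB-SIN sentences with adaptive SNR".

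The conditions are defined broadly: "Speech perception will be assessed in an aided (cochlear implant speech processor on) and unaided (cochlear implant speech processor off) condition". The listening conditions are "Cochlear implant only (contralateral ear masked"), contralateral ear only with the processor off, and combined. One of the noise arrangements is "Speech 0° azimuth and noise to contralateral ear".

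Section VI.C repeats the battery at 1, 3, 6, 9 and 12 months. Section VIII.B plans repeated-measures ANOVA in SPSS at p ≤ 0.05. Under VIII.B.1 it compares aided word and sentence scores across visits, and aided with unaided at each visit. Section VI.A.3 sets enrolment at 10.

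The documents give no score for a step not administered, no missing-data rule and no restriction of inference to ungated tests. They do not say whether the >50% rule applies per listening condition or per visit, or whether 'aided' in VIII.B.1 means implant-only, combined or both.

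**The concern.** A conventional repeated-measures ANOVA needs a score in every cell. Here a cell is empty because of the subject's own score on the easier step, so the loss depends on outcome by design. For a gated score, the analysed group can be a subset of the 10.

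Two comparisons are mainly exposed.

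(a) Implant-only sentence scores over time, if 'aided' includes implant-only. Section X.A.2 foresees sound quality too poor for speech perception. Those lost are the weaker scorers, so the analysed level is too high, and power falls below what 10 subjects already allow.

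(b) On versus off at SNR+0, if the gate applies per listening condition. A pair is lost when either score fails, and that is mainly the processor-off score. It is probably most exposed when noise is directed at the contralateral ear, the only hearing ear with the processor off. Those lost are not necessarily poor implant performers.

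**Working it through.** **Step 1: which scores are gated (from VI.C.3.b).** Gated: HINT and AzBio in quiet, and both at SNR+5 and SNR+0. Not gated: CNC, CID, BKB-SIN, SNR+10, localization and the questionnaires. Combined and contralateral-only scores in quiet should rarely fail, because entry requires a contralateral CNC score of at least 80% (VI.A.1).

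The plan states no score distribution, pass rate or power, so there is no figure of its own to reproduce. Every input in Steps 2 to 4 is assumed, and every result is complete-case.

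**Step 2: subjects complete at all five visits.** If a subject passes at each visit with probability p, the expected number complete of 10 lies between 10·p⁵ (independent visits) and 10·p (fully dependent visits). At p = 0.90 that is 10 × 0.59 = 5.9 to 9.0. With an equicorrelated normal latent score, and the chance that all 10 are complete = (share complete)¹⁰:

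| Per-visit pass rate | 80% | 90% | 95% | 99% |
|---|---|---|---|---|
| Complete, visit correlation 0.5 | 5.1 | 7.1 | 8.3 | 9.6 |
| Complete, visit correlation 0.7 | 5.9 | 7.6 | 8.7 | 9.7 |
| Complete, visit correlation 0.9 | 6.9 | 8.3 | 9.1 | 9.8 |
| All 10 complete, correlation 0.7 | 0.5% | 6% | 24% | 72% |

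**Step 3: implant-only AzBio in quiet over time.** Assumed: five visits at 0, 40, 70, 90 and 100% of the gain; visit correlation 0.7; HINT 8 points easier with extra noise SD 7; scores clipped to 0–100; AzBio observed if HINT >50; CID gate ignored. Power is for a one-way repeated-measures ANOVA in 10 subjects with sphericity assumed; trials with fewer than 2 complete subjects count as not significant.

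| Mean at 1 to 12 months, SD | Complete | Gain, complete vs true | 12-month level, complete vs true | Power, complete vs all tested |
|---|---|---|---|---|
| 35 to 55, SD 20 | 25% | 16.4 vs 19.6 | 74 vs 55 | 20% vs 96% |
| 50 to 65, SD 20 | 51% | 12.8 vs 14.7 | 76 vs 65 | 33% vs 76% |
| 60 to 75, SD 15 | 80% | 13.9 vs 14.7 | 78 vs 75 | 84% vs 95% |
| 70 to 80, SD 12 | 96% | 9.6 vs 9.8 | 80.4 vs 79.7 | 82% vs 84% |

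In the first row, about 25% of trials have fewer than 2 complete subjects (binomial, n = 10, share 0.25: 0.75¹⁰ + 10 × 0.25 × 0.75⁹ = 0.056 + 0.188 = 0.244).

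The gain is short by 19.6 − 16.4 = 3.2 points at worst. The standard error of the true gain at n = 10 is about 20 × √(2 × 0.3)/√10 = 4.9 (4.8 after clipping), so the bias in change is below sampling error.

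Sensitivity: with the Greenhouse-Geisser correction, power down the rows is 6/18/75/73% complete-case against 92/66/92/77% with all tested. At visit correlation 0.9, sphericity assumed, the first row is 63% against 100%, and the last two rows lose nothing.

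**Step 4: on/off at SNR+0, gate applied per condition.** SRT is the signal-to-noise ratio giving 50% correct. Assumed: off-SRT SD 3 dB; implant benefit 3 dB (SD 2); P(correct) = 1/(1 + exp(−0.4 × (SNR − SRT))), a slope of 10% per dB; 100-item scores; gates at +10 and +5.

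| Mean off-SRT | Benefit in complete pairs | True benefit | Difference |
|---|---|---|---|
| +4 dB | 25.2 | 20.8 | +4.4 |
| +2 dB | 23.8 | 22.3 | +1.5 |
| 0 dB | 20.8 | 20.5 | +0.3 |
| −2 dB | 16.3 | 16.3 | 0.0 |

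At +4 dB, 62% pass with the processor off, 86% pass with it on, and 61% form a pair, so the off score decides nearly all losses. The sign depends on the model: at +4 dB the bias is +7.5 points if benefit correlates −0.5 with off-SRT, +0.6 at +0.5, and −1.1 at +0.7. If the combined score set one gate for both conditions, the four estimates would be 23.9, 23.4, 20.8 and 16.4.

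**The case against.** The strongest reply is that little of what the trial claims is at risk. Sections VII and IX.B claim only on versus off, and implant-only level over time is neither a claim nor an endpoint. The ungated measures can still be tested in every subject in follow-up. Both exposed comparisons are conditional on definitions that the protocol leaves open, and listwise deletion is an inference about the usual ANOVA routine, not protocol text. The inputs that give large effects have no support in the documents: the 35-to-55 case implies a month-1 pass rate of about 37%, and the +4 dB case has 38% failing with an ear that met the entry criteria. All of this stands, and it limits the severity.

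It does not remove the gap. VIII.B.1 takes in word and sentence materials without restriction, VII.A.1 proposes to demonstrate improved speech perception, and nothing says that inference rests on the ungated tests.

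A reader might infer three stronger things that the documents do not support:

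- That the on/off comparison discards poor implant users and so overstates benefit. The losses come mainly from the off score, and the bias can take either sign.
- That the change over time is seriously biased. In the cases run it is modest to negligible.
- That the primary effectiveness endpoint fails. It does not rest on gated scores alone.

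**Conclusion.** The concern holds in limited form and is minor to moderate. As written, the plan lets the gated HINT and AzBio scores be analysed in a subset of the 10 determined by those subjects' own scores. For implant-only scores over time, the effect is an inflated level and lost power: severe if typical scores are near the gate, negligible if they are well above it. For on/off at SNR+0, pairs may be lost, but neither the size nor the direction of any bias follows from the documents. The structural point rests on the text plus the usual complete-case behaviour of ANOVA. All magnitudes rest on assumed score distributions.

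**What to change.** In VIII.B.1:

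- Name the ungated measures already collected as the basis for speech inference: BKB-SIN in noise (combined versus contralateral-only, and over time), and CNC words with CID sentences in quiet (mainly implant-only over time).
- State whether 'aided' means implant-only, combined or both.
- Make all gated HINT and AzBio scores secondary and descriptive by a rule fixed in advance, with the number tested at each step, condition and visit. Label any p-value on them as conditional on having passed the gate.
- Do not let the ANOVA depend on whether every cell turned out to be filled. That would tie inference to good performance. It would also discard the test about 32% of the time where 96% are complete and the loss is negligible (1 − 0.96¹⁰ = 0.34 with the rounded share), and about 89% of the time where 80% are complete (1 − 0.80¹⁰ = 0.89).

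In VI.C.3.b, state whether the >50% rule applies per listening condition and per visit.

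Also report how many subjects left follow-up, including those whose participation ended under XIII.B for lack of auditory stimulation. They are missing from the ungated measures too, so the change of measure does not cure that loss.

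Cost: analysis and definition wording only, with no extra testing. Gated scores lose their unconditional p-values, including combined and contralateral-only quiet scores that would usually have been complete. CNC or CID may sit near floor in the implant-only condition or near ceiling in the combined one.

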All procedures will be conducted by UNC investigators, including board-certified otologists and an audiologist. Fully informed consent will be obtained from all subjects.

A. Participants

Subjects must meet the following inclusion criteria and not exhibit any of the exclusion criteria.

- 1. Inclusion Criteria
 - a. Scheduled to undergo a surgical procedure that will result in profound hearing loss in the surgical ear
 - i. Unilateral, vestibular schwannoma with planned translabyrinthine surgery or unilateral Meniere's disease with planned labyrinthectomy
 - ii. Diagnosed by UNC investigators
 - b. $PTA \le 35 \text{ dB HL}$ in the contralateral ear
 - i. No evidence of retrocochlear dysfunction
 - c. Unaided CNC word score $\ge 80\%$ in the contralateral ear
 - d. Greater than 18 years of age at implantation
 - e. Realistic expectations
 - f. Willing to obtain appropriate meningitis vaccinations
 - g. No reported cognitive issues
 - i. Pass the Mini Mental State Examination (MMSE) screener
 - h. Able and willing to comply with study requirements, including travel to investigational site
 - i. Obtain CDC recommended meningitis vaccinations prior to surgery
- 2. Exclusion Criteria
 - a. History of implantable technology in either ear, such as a boneconduction implant
 - b. Non-native English speaker
 - i. Speech perception materials are presented in English
 - c. Inability to participate in follow-up procedures (i.e., unwillingness, geographic location)
- 3. Enrollment
 - a. This study seeks to enroll ten (10) subjects.
- B. Timeline

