 - i. Medical Evaluation
 - a. This is standard of care.
 - b. Subject will be seen by the physician
 - ii. Audiologic Evaluation
 - a. Unaided air and bone conduction thresholds
 - i. Air-conduction assessed with insert phones
 - b. Initial Activation of External Speech Processor (approximately 2-4 weeks postoperatively)
 - i. Unaided air and bone conduction thresholds
 - a. Air-conduction assessed with insert phones
 - ii. Unaided word recognition with CNC words in both ears
 - a. Unaided word recognition testing is conducted in quiet in the effected ear
 - b. Masking will be presented to the contralateral ear if indicated
 - iii. Initial activation of external speech processor
 - a. Subjects will be fit with the commercially available MED-EL SONNET external speech processor (MED-EL Corporation, Innsbruck, Austria). Speech perception and localization measures will be conducted with the subject listening with the SONNET external speech processor for the aided conditions.
 - iv. Counseling on the external device and use
 - c. 1-month Post-Initial Activation
 - i. Completion of test battery listed in VI.C.
 - d. 3-months Post-Initial Activation
 - i. Completion of test battery listed in VI.C.
 - e. 6-months Post-Initial Activation
 - i. Completion of test battery listed in VI.C.
 - f. 9-months Post-Initial Activation
 - i. Completion of test battery listed in VI.C.

- g. 12-months Post-Initial Activation (study endpoint)
 - i. Completion of test battery listed in VI.C
- C. Test Battery

The following test battery will be completed at each post-initial activation interval (1, 3, 6, 9 and 12 months). All assessment and mapping will be conducted at the Carolina Crossing research lab by a board-certified audiologist.

- 1. Unaided Diagnostic Assessment
 - a. Air- and bone-conduction thresholds in both earsi. Air-conduction assessed with insert phones
 - b. Unaided word recognition with CNC words in both ears
 - a. Unaided word recognition testing is conducted in quiet in the effected ear
 - b. Masking will be presented to the contralateral ear if indicated
- 2. Tympanometry for each ear
- 3. Sound Field Measures

The Carolina Crossing research lab features a 180° arc with 11 speakers spaced 18° apart. This arc will be utilized during the speech perception and localization measures.

- a. Aided thresholds with the external speech processor on and masking applied to the contralateral ear will be measured using pulsed, warble tones

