 - 1. Demonstrate an improvement in speech perception abilities in an aided (cochlear implant on) versus an unaided (cochlear implant off) condition
 - 2. Demonstrate an improvement in localization abilities in an aided (cochlear implant on) versus an unaided (cochlear implant off) condition
 - 3. Demonstrate an improvement in subjective report in an aided (cochlear implant on) versus an unaided (cochlear implant off) condition

VIII. Statistical Analysis

- A. Descriptive summaries will be provided for the following: subject demographics, and frequency of major and minor complications/adverse events.
- B. A single-subject design will be utilized, where each subject serves as his or her own control, for analysis of objective and subjective results. A singlesubject design was chosen in order to accommodate the heterogeneity that is well known to characterize auditory prosthesis research. Repeated-measures ANOVA will be calculated with a p-value of ≤ 0.05 for statistical significance. Statistical analysis will be conducted with SPSS software.
 - 1. Comparison in aided speech perception performance on word and sentence materials in the post-initial activation intervals
 - a. Also compare the difference between the aided and unaided conditions at each follow-up interval
 - 2. Comparison in localization abilities in the post-initial activation intervals
 - a. Also compare the difference between the aided and unaided conditions for each follow-up interval
 - 3. Comparison in subjective report in the post-initial activation intervals

If needed, statistical consultation will be sought from the North Carolina Translational and Clinical Sciences Institute (TraCS) or UNC Odum Institute.

IX. Endpoints

- A. Safety endpoint
 - 1. The primary safety endpoint is the evaluation of Adverse Events. All Adverse Events will be reported to the UNC IRB. If the UNC IRB or study investigators deem an Adverse Event unacceptable, then this would be sufficient terms to terminate the study.
- B. Primary effectiveness endpoint

1. The primary effectiveness endpoint is the comparison of speech perception (VII.A.1), localization abilities (VII.A.2) and/or subjective report (VII.A.3) when the cochlear implant is on versus off.

X. Risk Analysis

A. Potential risks

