 - 3. Reports of pain from the external speech processor placement will be addressed by different wearing options (i.e. moleskin between the external speech processor and the subject's ear, or different battery-wearing options to lighten weight on the pinna).
 - 4. Mapping will be conducted at each post-initial activation interval to improve audibility and comfort of the sound quality from electric stimulation.
 - 5. The MED-EL cochlear implant has MRI limitations*. Subjects may have CT scans or x-ray imaging postoperatively.
 - a. *The MED-EL SYNCHRONY cochlear implant is approved for MRI up to 3 Tesla with the magnet in place (magnet can be removed to eliminate shadow if necessary).
 - 6. An otologist will conduct medical follow-up evaluations at the 3, 6 and 12-month intervals which is standard of care for cochlear implant recipients.

XI. Potential Benefits

- A. Improvement in speech perception abilities in noise with the cochlear implant due to utilization of auditory cues from both ears.
- B. Improvement in localization abilities with the cochlear implant due to utilization of auditory cues from both ears.
- C. Improvement in subjective benefit with the cochlear implant as compared to an unaided condition.

XII. Adverse Events

A. Anticipated versus Unanticipated Events

- 1. Anticipated Events: those events described as potential risks (section X.A.) of the protocol.
- 2. Unanticipated Events: events not reported as potential risks (section X.A.).
 - a. Unanticipated serious adverse events are defined as any serious adverse event related to the health or safety or any life-threatening problem or death caused by, or associated with, a device, if that event, problem, or death that was not previously defined in nature, severity, or degree of incidence in the literature or investigational plan. It can also include any other unanticipated serious problem associated with a device that relates to the rights, safety or welfare of subjects.
- B. Reporting adverse events
 - 1. Anticipated events will be reported to the FDA in the annual report
 - 2. Unanticipated events will be reported to the FDA and UNC IRB within 10 days of the investigator becoming aware of the event, as required by 21CFR 812.150.

XIII. Monitoring

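### Localization is tested at a single sound level, so with the implant off loudness at the hearing ear can partly indicate direction and make the on-versus-off contrast less sensitive

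*Combined protocol and SAP*

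**What the plan says.** Section VI.C.3.c.i sets the stimulus: "The stimulus is a 200-ms speech-shaped noise, presented at 70dB-SPL from one of the 11 speakers". What varies between trials is the source: "from one of the 11 speakers (evenly spaced -180 to 180 degrees), selected at random". No section mentions varying the level or otherwise making overall loudness uninformative. The published method cited in VI.C.3.c.iii is attached to the error analysis, not to how the sound is presented. Subjects are not told whether their answers are correct (VI.C.3.c.ii).

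The two listening conditions (VI.C.3.c.iv) are the hearing ear alone with the processor off, and both ears with the processor on. The hearing ear must have a pure-tone average of 35 dB HL or better (VI.A.1.b). The battery is run at 1, 3, 6, 9 and 12 months.

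The related claim is VII.A.2: "Demonstrate an improvement in localization abilities in an aided (cochlear implant on) versus an unaided (cochlear implant off) condition". Localization is one of three domains in the primary effectiveness endpoint (IX.B). Section XI.B, under Potential Benefits, gives the expected mechanism: "Improvement in localization abilities with the cochlear implant due to utilization of auditory cues from both ears".

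**The concern.** The head attenuates sound arriving from the far side. The plan itself treats side as important when it moves the noise between the implanted and the hearing side in the speech tests (VI.C.3.b.ii). If every trial has the same source level, loudness at the hearing ear varies with direction. A subject with the implant off can then solve part of the task with one ear.

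Two things are at stake. First, any use of the cue lowers off-condition error and narrows the on-versus-off difference, in a study of ten subjects with no power calculation. Second, at a fixed level the on-condition score can also draw on absolute loudness at either ear, so an observed gain does not by itself show comparison between the ears.

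**Working it through.** The documents give no expected localization error, SD or effect size, so there is no planned figure to reproduce. The calculation below illustrates how large the effect could be.

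**From the documents:** 11 speakers, 18° apart, on a 180° arc (VI.C.3), taken here as −90° to +90°; one level, 70 dB SPL; ten subjects (VI.A.3); significance at 0.05 (VIII.B).

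**Assumed, not in the documents:** level change H across the arc at an ear; internal level noise (SD) at the hearing ear and at the implanted ear; SD of the on-minus-off difference; a listener who knows exactly which level goes with which direction.

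**Reference values.** Always answering the centre speaker gives RMS error √(mean θ²) = √[18² × 2(1+4+9+16+25)/11] = √3240 = 56.9°. Uniform guessing gives √(2 × 3240) = 80.5°.

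**Model.** Level heard = random level shift + direction effect + noise. The shift is 0 at fixed level, or uniform on ±5 or ±10 dB. The listener answers with the posterior mean direction.

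**Off-condition error, linear relation of level to direction.** With H = 8 dB and noise 2 dB: 34° at fixed level, 46° with ±5 dB, 52° with ±10 dB. Against the no-information value of 57°, ±5 dB removes (46 − 34)/(57 − 34) = 52% of the cue's advantage, and ±10 dB removes (52 − 34)/(57 − 34) = 78%. With H of 5, 8 or 12 dB and noise of 1 to 3 dB, fixed-level error runs from 14° to 50°, against 47° to 55° with ±10 dB.

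**On-versus-off gain, separate model with a sine relation.** H = 8 dB, noise 2 dB at the hearing ear and 3 dB at the implanted ear:

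| Level | Off | On | Gain |
|---|---|---|---|
| Fixed | 31.1° | 27.3° | 3.8° |
| ±5 dB | 43.8° | 28.4° | 15.4° |
| ±10 dB | 50.4° | 28.8° | 21.6° |

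Varying the level mainly raises the off error; the on error hardly moves. Over 18 settings (H of 4, 8 or 12 dB; noise of 1, 2 or 4 dB at the hearing ear and 3 or 6 dB at the implanted ear) the gain ranged from 0.2° to 11.3° at fixed level, 2.2° to 16.8° with ±5 dB and 3.0° to 26.3° with ±10 dB. It was larger with a varied level in every setting.

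**Power.** Two-sided paired t test, n = 10, noncentrality (gain/SD) × √10, 9 degrees of freedom:

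| Assumed SD of difference | Gain 5° | Gain 15° | Gain 20° |
|---|---|---|---|
| 10° | 0.29 | 0.99 | 1.00 |
| 15° | 0.16 | 0.80 | 0.96 |
| 20° | 0.11 | 0.56 | 0.80 |

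At an SD of 15°, a gain of 3.8° has power below 0.16, and gains of 15.4° and 21.6° have power of at least 0.80.

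**Imperfect calibration.** Give each listener a fixed error in the reference level, with SD 3 or 5 dB (assumed). In the linear case with H = 8 dB and noise 2 dB, fixed-level off error rises from 34° to about 51° or 62°. That is close to the 52° of a calibrated listener at ±10 dB, or worse than always answering centre. The advantage of varying the level then shrinks, and in some settings it vanishes or reverses.

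**Speaker span.** VI.C.3 says the room "features a 180° arc with 11 speakers spaced 18° apart": 10 gaps × 18° = 180°. The span in VI.C.3.c.i implies 360°/10 = 36° between speakers. Both cannot describe the same array.

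**The case against.** The strongest objection concerns size. The modelled listener has a perfect map from loudness to direction, but the plan gives no feedback and describes no training. Repetition over five visits does not directly teach that map, although a subject could partly self-calibrate from the range of loudness heard. Every quantity that drives the degree figures is assumed. This stands: the figures bound what the cue could do and do not predict what it will do.

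A reader might infer that a fixed level could produce a spurious benefit, or that the plan's tested claim is a two-ear mechanism. The documents support neither. The off-condition cue reduces the apparent benefit, and VII.A.2 claims only improvement with the implant on. The two-ear attribution appears only in XI.B, which is not an endpoint. Localization is also joined to speech perception and subjective report by an and/or in IX.B, so lost sensitivity here does not decide the trial.

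A fixed level is also a legitimate and simpler choice, with the same stimulus in both conditions. The Introduction already describes one-ear localization as variable, so the plan does not assume chance performance with the implant off. That does not remove the cue from the contrast.

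**Conclusion.** The point holds as a measurement refinement. One level is specified, only the speaker is randomised, and loudness at the hearing ear can therefore carry direction when the implant is off. The consequences are lost sensitivity in the localization contrast and unclear attribution of any gain.

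The size is unknown. For an assumed 8 dB range and 2 dB noise, the rise in off-condition error from about 34° to 52° with a ±10 dB variation is an upper bound, reached only by a perfectly calibrated listener. The effect is zero for a subject who ignores loudness. The power figures rest on a further assumed SD. It would be wrong to read any of these degrees as the expected bias in this trial.

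**What to change.** In VI.C.3.c.i, state that the presentation level varies at random from trial to trial around 70 dB SPL over a named range, identically in the on and off conditions and at all visits, and that error is pooled over levels. Choose a range that stays audible to the hearing ear and the processor. A ±10 dB range would reach down to 60 dB SPL, the level already used for speech in VI.C.3.b; a ±5 dB range is gentler but leaves more of the cue. If the laboratory already varies the level, saying so is enough.

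In the same sentence, reconcile the stated speaker span with the 180° arc in VI.C.3.

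The cost is a setting in the presentation software. The drawbacks are a slightly harder task and less direct comparison with fixed-level data from elsewhere.

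### Subjective report is claimed with the implant on versus off, but no implant-off or pre-activation SSQ/APHAB rating is specified and the analysis compares only post-activation visits

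*Combined protocol and SAP*

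**What the plan says.** **The claim.** Section VII.A.3 aims to "Demonstrate an improvement in subjective report in an aided (cochlear implant on) versus an unaided (cochlear implant off) condition". The primary effectiveness endpoint in IX.B.1 covers speech perception, localization "and/or subjective report (VII.A.3) when the cochlear implant is on versus off". Section XI.C lists as a potential benefit: "Improvement in subjective benefit with the cochlear implant as compared to an unaided condition".

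**Data collection.** VI.C.3.b states: "Speech perception will be assessed in an aided (cochlear implant speech processor on) and unaided (cochlear implant speech processor off) condition". VI.C.3.c states: "Localization will be assessed in an aided (cochlear implant speech processor on) and unaided (cochlear implant speech processor off) condition". VI.C.4 then names the SSQ and APHAB with no listening condition. VI.C and Appendix B place the questionnaires at 1, 3, 6, 9 and 12 months after activation. The audiologic lists for the preoperative visit (VI.B.2.b) and the activation visit (VI.B.4.b) contain no questionnaire.

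**Analysis.** VIII.B makes each subject his or her own control, for subjective as well as objective results, using repeated-measures ANOVA at 0.05. Under speech, VIII.B.1.a adds: "Also compare the difference between the aided and unaided conditions at each follow-up interval". Under localization, VIII.B.2.a adds: "Also compare the difference between the aided and unaided conditions for each follow-up interval". For subjective report, VIII.B.3 reads in full: "Comparison in subjective report in the post-initial activation intervals". It has no sub-item.

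**The concern.** The comparator for subjective report is named three times (VII.A.3, IX.B.1, XI.C), but the plan does not say when or how it is rated, and VIII.B.3 does not use it. What VIII.B.3 does test is whether scores change between month 1 and month 12.

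The two questions can give different answers in both directions. Benefit already present at month 1 and then held would give a flat profile, which could be misread as no benefit. A rise from month 1 to month 12 would not by itself show that listening with the implant on is better than with it off.

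VII.A.3 is stated as a claim in its own right, so it needs data and an analysis even if the overall endpoint is met on speech or localization.

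**Working it through.** **Step 1: set the three domains side by side.** The plan gives no figure to reproduce here, so the check is a comparison of sections.

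| | Speech | Localization | Subjective report |
|---|---|---|---|
| On/off claim | VII.A.1 | VII.A.2 | VII.A.3 |
| Off condition named in the test battery | yes, VI.C.3.b | yes, VI.C.3.c | no, VI.C.4 |
| Aided-versus-unaided analysis line | yes, VIII.B.1.a | yes, VIII.B.2.a | no, VIII.B.3 |
| Scheduled visits before activation | 0 | 0 | 0 |
| Scheduled visits after activation | 5 | 5 | 5 |

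Speech and localization also have no pre-activation measurement, but they do not need one, because the off condition is measured at each visit. Two of the three components therefore have both the data and the analysis; subjective report has neither. VI.B.4.b.iii does mention aided conditions, but only for speech and localization.

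**Step 2: what the VIII.B.3 test can detect.** The following is an illustration only. The sample size (n = 10, VI.A.3), the five intervals and the 0.05 level come from the plan. The benefit D, the fraction f of it already reached at month 1, and the SD are assumed, because the documents give none.

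Assume compound symmetry and an SD of 1 for a paired difference, so the error variance is 0.5. Assume no drift in off-state ratings, and let mean benefit rise in four equal steps from fD at month 1 to D at month 12. Each step is (1 − f)D/4 and the five means lie −2, −1, 0, 1 and 2 steps from their average, so

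- Σ(μⱼ − μ̄)² = 10 × [(1 − f)D/4]² = 0.625(1 − f)²D²
- noncentrality λ = 10 × 0.625(1 − f)²D² / 0.5 = 12.5(1 − f)²D²
- power = P(noncentral F with 4 and 36 df, noncentrality λ, exceeds 2.634)

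For example, D = 1 and f = 0.5 give λ = 12.5 × 0.25 = 3.125 and power 22.6%.

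| D (SD units) | f = 0 | f = 0.25 | f = 0.5 | f = 0.8 | f = 1 |
|---|---|---|---|---|---|
| 1.0 | 76% | 48% | 23% | 7% | 5% |
| 1.5 | 99% | 86% | 48% | 10% | 5% |
| 2.0 | >99% | 99% | 76% | 15% | 5% |

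At f = 1, λ = 0 for every D, so the rejection rate is the significance level. Simulation with 40,000 runs and a constant benefit of 0, 1, 2 or 5 SD rejected in 5.1%, 5.0%, 5.1% and 4.9% of runs.

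**Step 3: what an on/off comparison could detect.** A two-sided paired t test at month 12 has 9 df and noncentrality (D/SD) × √10. With an on/off difference SD of 1, power is 80%, 99% and >99% for D = 1.0, 1.5 and 2.0, whatever f is. With an SD of 1.5 or 2, power at D = 1.0 falls to 47% or 29%.

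**The case against.** The strongest reply concerns weight. IX.B.1 joins the three domains by and/or, and speech and localization are fully specified, so the primary endpoint can be assessed without the questionnaires. That stands, and it limits the reach of the point. It does not rescue VII.A.3, which is unconditional.

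A second reply is that IX.B.1 names the contrast and VIII.B supplies the own-control design and the ANOVA, so only an operational line is missing. The contrast and the general method are indeed stated. But neither section creates an off-state rating, and the one specific rule for subjective report, VIII.B.3, describes a different comparison.

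A third reply is that the questionnaires may be intended to be answered separately for aided and unaided listening. The documents do not exclude this, so the accurate statement is that an off-state rating is not specified, rather than that it will not be taken. If it is intended, it has to be written down and analysed.

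On the power figures, the contrast depends on f, for which the documents give no value. If none of the benefit is present at month 1 (f = 0), the VIII.B.3 test has 76% power at 1.0 SD, close to the paired test's 80%. The paired figures also need an on/off difference SD of 1, which is optimistic if benefit varies between subjects, as the heterogeneity noted in VIII.B suggests. Both reservations are accepted; the finding rests on the comparison of sections, not on these figures.

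**Conclusion.** The concern holds and should be fixed. A stated claim, which is also one of the three components of the primary effectiveness endpoint, has no specified comparator rating and no matching analysis. This follows from the text alone and needs no assumption.

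The size of the consequence depends on how early benefit appears. With stable benefit from month 1 and no drift in off-state ratings, the VIII.B.3 test has about a 5% chance of significance at any benefit. With half the benefit present at month 1, the illustration gives 23% to 76% for benefits of 1.0 to 2.0 SD. Whatever its power, a significant VIII.B.3 result would be evidence of change over time, not of an on/off difference. The speech and localization components are unaffected.

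**What to change.** **Preferred, keeping the stated endpoint.** State in VI.C.4 that the SSQ and the APHAB are each rated for processor-on and processor-off listening at every interval. Add an item VIII.B.3.a with the wording already used for speech: "Also compare the difference between the aided and unaided conditions at each follow-up interval". VII.A.3, IX.B.1, XI.C and the visits marked in Appendix B then need no change. The line gives 5 intervals × 2 instruments = 10 comparisons, with a chance of at least one false positive of up to about 40% if they were independent (1 − 0.95¹⁰ = 0.40). It would help to name month 12, already the study endpoint in V.C, as the main time point.

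Cost: 5 visits × 2 instruments = 10 extra ratings per subject, or 100 over 10 subjects, if one rating per instrument per visit is now taken. It can be introduced at any later visit. The drawbacks are subject time, and that subjects may seldom experience the off state they are asked to rate.

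**Alternative or supplement.** Give both questionnaires at the activation visit before the processor is switched on. Add them to VI.B.4.b ahead of item iii and to Appendix B, and add to VIII.B.3 a paired within-subject comparison of each interval with the pre-activation score. A preoperative score could be added to VI.B.2.b and Appendix B for description only, since it precedes the surgical hearing loss. If this replaces the on/off contrast, VII.A.3, the subjective part of IX.B.1 and XI.C must be reworded to compare listening with the implant against pre-activation.

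Cost: 2 extra questionnaires per subject (20 in all), or 4 (40 in all) with the preoperative score. The comparison becomes a change over time, and a score taken about 2 to 4 weeks after surgery may partly reflect surgical recovery. Unlike the preferred fix, this one must be in place before subjects are activated.
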